## **2.0 OBJECTIVES**

We propose a 3-group, 12-month (6 mos. of exercise training + 6-mo. follow-up) randomized trial in 294 couples comparing a supervised group program of *Exercising Together* to: 1) separate supervised group exercise (survivor-only and spouse/partner-only classes) and 2) separate unsupervised exercise where survivors and spouses/partners exercise on their own at home. We hypothesize that *Exercising Together* will significantly improve physical, mental and relationship health of couples more than separate exercise performed in a group or home setting and that benefits will persist long-term. The study addresses the following aims:

**Aim 1:** Determine the efficacy of *Exercising Together* on relationship quality (intimacy, communication and incongruence) in couples coping with PC, BC, or CRC.

**Aim 2:** Determine the efficacy of *Exercising Together* on the physical health (body composition, lipids, insulin resistance, blood pressure, inflammation, and physical function) and mental health (anxiety, depressive symptoms, fear of recurrence) of both the survivor and spouse/partner.

**Aim 3:** Determine how long individual and couple-level benefits from *Exercising Together* last.

**Aim 4 (Exploratory):** Identify the types of couples that benefit most from *Exercising Together*.

**Ancillary study:** We have received supplemental funding to conduct a pilot study with the following aim: Assess the feasibility and acceptability of remotely delivered supervised, group-based exercise to couples coping with cancer living in geographically underserved counties in Oregon. We will recruit an additional cohort of 30 couples (60 participants) coping with breast, prostate or colorectal cancer residing in five geographically underserved counties in Oregon (Wheeler, Malheur, Jefferson, Lake, and Benton counties). Data collected from the ancillary study will not be combined with data from the parent trial. Instead, data from the ancillary study will be compared to data collected in the parent trial to evaluate accrual, retention, and adherence rates, safety, intervention fidelity, and proportion of testing visits and measures completed. The ancillary

study will use separate recruitment materials, consent forms, and telephone screening scripts from the parent trial.

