### **3.0 STUDY DESIGN/METHODOLOGY**

The *Exercising Together* trial is a single-blind, parallel group, randomized trial comparing 3 arms: Arm 1 (experimental): *Exercising Together* where couples perform partnered exercise in a supervised, group setting versus two comparator conditions where survivors and spouses/partners perform exercise routines separately in either a supervised group setting (Arm 2) or unsupervised at home (Arm 3). All three arms will train for a 6-month period and then be followed up 6 months later. Data will be collected at baseline, 3, 6 and 12 months.

Ancillary study: Participants who enroll in the ancillary study will not be randomized. Eligible couples who agree to participate in supervised exercise will be assigned to the *Exercising Together* program. Eligible couples who decline to participate will be offered the option to enroll in the Survivor / Spouse/Partner Home Training program.

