Aim 1: Determine the efficacy of partnered strength training on relationship quality (intimacy, communication and incongruence). A longitudinal multivariate-outcomes dyad model will be used to directly examine couple trajectories in intimacy (emotional & physical) and communication over time. This is a multi-level model where responses from the survivor and spouse/partner are modeled simultaneously to control for the interdependent nature of the data and autocorrelation among repeated assessments. These models have been described and used extensively by Co-PI [name].[22, 111-113] The Level 1 model has four coefficients representing intercepts (baseline assessments) and slopes (rates of change) for survivors and spouses/partners that become outcome variables in a Level 2 model. Models with linear and quadratic change across time will be compared to determine best fit to the data. Aim 1 will be addressed with Level-2 models that include dummy variables to directly examine the effects of the partnered intervention vs. supervised individual (dummy 1) and unsupervised individual (dummy 2) exercise groups on individual level changes (controlling for couple effects) in intimacy and communication across time. A significant group coefficient on the slopes at level 2 and significantly better fitting model (evidenced by deviance statistic) will indicate the rate of change across time is different depending on a treatment group (i.e., interaction effect). We will also explore the efficacy of *Exercising Together* on incongruence (regarding survivor pain & fatigue) in couples. Univariate-outcomes models will be used to generate Empirical Bayes estimates of the gap between survivor and spouse/partner over time for each symptom measure. This comprehensive approach to estimating incongruence has been described elsewhere[114-116] and successfully used by this team.[55, 63, 113, 117, 118] The effect of *Exercising Together* on incongruence will be directly tested (similar to above model) by a significant coefficient for one of the two GROUP variables on the slope parameter and significantly better fitting model.

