Aims 2: Determine the efficacy of partnered strength training on physical and mental health. Separate longitudinal multivariate-outcomes models will be used to directly examine the effect of partnered strength training in couples on each physical (body composition, lipids, insulin resistance, blood pressure, inflammation, and physical function) and mental health outcome (anxiety, depressive symptoms, fear of recurrence) as described above under Aim 1.

Aim 3: Determine the persistence of Exercising Together. Sustained effects will be tested by comparing linear and quadratic trajectories across time (as discussed above). We will also separately estimate and directly compare the intervention effects between the intervention (baseline to 6 months) and follow-up (6 months to 6 months after end of intervention) periods.

Aim 4: Exploratory analyses: Patterns and predictors of types of couples who benefit the most. GMM identifies distinct patterns of change that vary around different means, have unique variance and homogenous within-trajectory growth. Based on conditional probabilities, cases are assigned to the “most likely class” or pattern of change over time (e.g., couples who benefit/improve most from the intervention). Couple-level estimates from Aims above will be integrated into progressive GMM to determine if there are distinct and naturally-occurring patterns of change in outcomes over time with the dyad as the unit of analysis. Survivor-, spouse/partner- and couple-level

determinants of fitting one pattern of change over the other(s) will be modeled using logistic, multinomial or ordinal regression as appropriate. This integrated multilevel and mixture modeling approach has been used previously by this team,[118] as it allows us to identify types of dyads and differentiate them based on individual and couple-level factors. Finally, based on our pilot, we expect the intervention to have a positive effect on relational outcomes although it is possible that in a larger trial a small subgroup of couples will experience poorer outcomes; identifying characteristics of each common type of couple will allow interpretation of the generalizability of our findings.

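### Aim 3's two named tests of persistence do not by themselves distinguish a benefit kept to month 12 from one that is lost

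*Combined protocol and SAP*

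**What the plan says.** Aim 3 in section 2.0 reads "Determine how long individual and couple-level benefits from" the program last, and the trial hypothesis there includes "that benefits will persist long-term".

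The test is given in section 13.0, Analysis Plan, Aim 3: "Sustained effects will be tested by comparing linear and quadratic trajectories across time (as discussed above". The text it points back to, under Aim 1, uses that comparison only to choose the form of time: "Models with linear and quadratic change across time will be compared to determine best fit to the data". The Aim 1 criterion for an arm effect is a significant group coefficient on the slope together with a better-fitting model, which "will indicate the rate of change across time is different depending on a treatment group (i.e., interaction effect".

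Aim 3 then adds a second element: the team will "separately estimate and directly compare the intervention effects between the intervention (baseline to 6 months) and follow-up", the latter running from month 6 to month 12.

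Section 3.0 (Six-Month Follow-Up Period) says the month-12 measures serve to assess residual effects, and that exercise and shared activities at months 9 and 12 will be considered in the Aim 3 analysis. No section names a between-arm contrast at month 12 or says which result would count as a sustained benefit.

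**The concern.** A benefit gained by month 6 and held to month 12 rises and then flattens. A benefit gained by month 6 and then lost rises and falls. Both paths bend downwards, so both favour a quadratic over a straight line. The period comparison, read as change within each period, behaves in the same way: with full retention the arm effect is positive in the first period and zero in the second, and with full loss it is positive and then negative. The two periods are unequal either way.

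At stake is the reading of one of the three main aims. A significant quadratic term or unequal period effects could be reported as fading when the benefit was fully kept, or as a sustained effect when it had gone. With no stated rule, the choice could be made after the data are seen.

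**Working it through.** **Inputs from the documents**
- Visits (section 3.0): "Data will be collected at baseline, 3, 6 and 12 months".
- 264 analysed couples, d = 0.40, power 0.80, 10% attrition, 294 randomised (section 13.0, Power and Sample Size).
- Three arms with even enrolment (section 8.0): 264 / 3 = 88 couples per arm.

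**Assumptions, not in the documents:** even gain up to month 6; outcomes in SD units; two-sided 5% level; equal correlation between all visits of 0.5, 0.7 or 0.85; one partner role considered at a time.

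**The plan's own figure.** 264 / 0.90 = 293.3, rounded up to 294, which reproduces. The 0.80 power cannot be rebuilt because the significance level and variance components are not given. The signs and ratios in steps 1 to 4 do not depend on it.

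**Step 1. Profile.** Let the between-arm difference be 0, d/2, d and r·d at months 0, 3, 6 and 12, where r is the share of the month-6 benefit still present at month 12.

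**Step 2. Linear versus quadratic.** The least-squares quadratic coefficient at these four visits is (7·y0 − 4·y3 − 8·y6 + 5·y12) / 396 per month squared. Substituting gives (−2d − 8d + 5rd) / 396 = −5·d(2 − r) / 396.

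**Step 3. Period comparison as change within period.** (d − 0) − (rd − d) = d(2 − r).

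Both tests therefore measure the same quantity, d(2 − r). It is zero only if d = 0 or r = 2, that is, if there was no benefit or the advantage kept growing at the same pace after training stopped. With d = 0.40:

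| Month-12 state | r | Quadratic term | Period difference | 6–12 change | 0–12 change |
|---|---|---|---|---|---|
| Fully kept | 1 | −0.0051 | 0.40 | 0 | 0.40 |
| Half lost | 0.5 | −0.0076 | 0.60 | −0.20 | 0.20 |
| Fully lost | 0 | −0.0101 | 0.80 | −0.40 | 0 |
| Still growing | 2 | 0 | 0 | +0.40 | 0.80 |

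**Step 4. Does size help?** Take d = 0.20, fully lost (r = 0): d(2 − r) = 0.40 and the quadratic term is −5 × 0.40 / 396 = −0.0051. These equal the values for d = 0.40, fully kept.

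**Step 5. Precision of the separate 6-to-12-month estimate.** The SE of the between-arm difference in change is √(4(1 − ρ)/88):
- ρ = 0.5: SE 0.151, half-width 1.96 × 0.151 = 0.30, or 74% of 0.40.
- ρ = 0.7: SE 0.117, half-width 0.23, or 57%.
- ρ = 0.85: SE 0.083, half-width 0.16, or 40%.

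**The case against.** A reader might infer that the tests give one and the same signal in both cases, and that Aim 3 as planned cannot be answered. The documents do not support that, for three reasons.

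First, the same Aim 3 text promises separate period estimates as well as their comparison. The 6-to-12-month estimate is 0 if the benefit is kept and −0.40 if it is lost. Under the assumptions above, full loss would be detected with power 0.76, 0.93 or 0.998 at correlations of 0.5, 0.7 and 0.85. The fitted quadratic curves differ too, with a 0-to-12-month change of about +0.415 if kept and +0.029 if lost. This stands. What remains is that the plan does not make that estimate the test. The plan does not say that a non-significant value will be called maintenance, but it gives no other rule, and step 5 shows how much loss such a value could hide.

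Second, the two tests share direction, not size: both quantities double when the benefit is lost. This also stands, but size helps only when read against the month-6 effect, as step 4 shows.

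Third, the effect in the follow-up period could mean the arm difference at month 12. The comparison would then be 0.40 with 0.40 if kept and 0.40 with 0 if lost, which does discriminate. The plan does not define the term. Its description of each period by start and end points favours change within period but does not settle it.

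It is also tempting to take an SE from the stated power (0.40 / 2.80 = 0.143) and quote one figure, 1.96 × 0.143 = 0.28, or 70% of the benefit. That power statement concerns change over time with four measurements, not a two-visit contrast, so only the range in step 5 is defensible.

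**Conclusion.** The concern holds for the two named tests. Linear-versus-quadratic fit, and the period comparison read as within-period change, point the same way whether a month-6 benefit is kept, half lost or fully lost. A fully kept 0.40 and a fully lost 0.20 cannot be told apart on either. This is a stated test that does not match its aim, not only a missing detail. It does not extend to everything Aim 3 will produce, because the separate 6-to-12-month estimate is informative.

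The signs and the factor of two rest only on an even gain up to month 6. The power and interval figures also rest on 88 couples per arm and the assumed correlations and significance level. The point should be addressed before analysis, but it does not put the design in doubt.

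**What to change.** In section 13.0, Aim 3, name the persistence test: the between-arm difference (Arm 1 v Arm 2, and Arm 1 v Arm 3) in change from baseline to month 12, with 95% CI. Estimate it in the planned dyad model with time as categories, or with two pieces joined at month 6, where it is the sum of the two period effects. Under the assumptions above it is significant with probability 0.76, 0.93 or 0.998 if a 0.40 benefit is kept, and 0.05 if it is lost.

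Report beside it, as a co-reported estimate and not only as description, the between-arm change from month 6 to month 12 with its 95% CI, and read both with the month-6 effect. This is needed because the 0-to-12-month contrast alone cannot tell a retained benefit from one that first appears after month 6, and a non-significant value does not prove loss. A claim of retention based on the 6-to-12-month change would need a margin stated in advance.

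Keep the linear-versus-quadratic comparison only for choosing the shape of time. Do not use it, or equality of the two period effects, as the test of sustained benefit.

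Cost: SAP wording and slightly more analysis, with no new visits or data.

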## 13.0 BIO-STATISTICAL CONSIDERATIONS

### Power and Sample Size

Required sample size was derived for the outcomes of Aim 1. Power analysis using traditional assumptions of the repeated measures ANOVA model suggest that as few as 174 couples would be necessary to detect a small effect ( $d=.20$ ) between groups over time, an effect smaller than the observed effect on affectionate behavior in spouses/partners in our previous work[40]. However, these traditional power calculations are known to be optimistic. While there are good power formulae for MLM clustered designs and repeated measures designs, as yet there is no specific formula for calculating power for dyadic analyses. Using a formula provided by Raudenbush and Bryk[104, 105] for individual repeated measures and estimates from our previous dyadic models, we calculate a sample of 264 couples measured 4 times over a 12-month period has a power of 0.80 to detect a moderate effect ( $d=.40$ ) on change over time. As dyad models using MLM control for interdependence between members of the couple, power is increased over an individual model. We, therefore, believe this to be a more conservative estimate of power. Further attempts to increase power and reduce Type I error will be to use the omnibus hypothesis-testing procedure in the HLM program. Another rule-of-thumb is to require a minimum number of subjects per parameter estimated. Even in the most complicated model, the proposed sample of 264 couples would exceed the minimum standard of 5-10 subjects per parameter estimated.[106] No universal approach has been adopted for sample size considerations in GMM and this will be used in an exploratory aim; however, our n-to-items ratio exceeds sample size recommendations for related approaches (10-20:1).[107] In sum, the proposed sample size of 264 couples is on par with our previous trials and will allow us to detect clinically meaningful change and address study aims. To insulate the sample size against an estimated attrition of 10% across the study period, 294 couples will be randomized. The attrition estimate is more conservative than our prior trial of *Exercising Together* where no couples in the exercise program dropped out and the drop out in our current GET FIT trial that average 6% for a 6-month intervention. Couples will be enrolled into 10 waves (a new wave begins every 3-4 months) of 9-10 couples to maintain reasonable class sizes and make efficient use of testing resources. We will recruit approximately even numbers of couples coping with each type of cancer (N=98 per disease site) and stratify by cancer type at randomization.

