
### Analysis Plan

Standard descriptive statistics/graphics will be used to check for any departures from statistical assumptions (e.g., normality, outliers, etc.).[108] We will examine dropout and patterns of missing data to determine mechanisms (MCAR, MAR, or not ignorable). In the case of data missing MCAR or MAR, model-based maximum likelihood estimation available in the MLM approach will allow unbiased parameter estimation using all available data (i.e., missing data is handled efficiently

with no loss of information). If the rate of attrition is high and missing data is not ignorable, we will continue with the planned analyses but temper our conclusions. For each aim, we will conduct intention-to-treat (ITT) and completers only analyses. ITT analyses will include all participants regardless of adherence to exercise regimen. Based on median attendance data from our prior trials, completers will be defined as participating in 50% or more of the scheduled exercise sessions. We will track medical treatment changes, cancer recurrence, and adherence to exercise. Age, comorbidities and time since diagnosis will be considered as covariates in all analyses. All analyses will be conducted in R and HLM statistical software packages (Aim 4 will be conducted using MPlus v7.2).

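### Aim 4, as written, regresses each couple's modal trajectory class on predictors with no allowance for classification error, which can bias the predictor effects

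*Combined protocol and SAP*

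**What the plan says.** The Aim 4 paragraph of the Analysis Plan (Section 13.0) describes three steps.

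- Input: "Couple-level estimates from Aims above will be integrated into progressive GMM", with the dyad as the unit of analysis.
- Classification: "Based on conditional probabilities, cases are assigned to the “most likely class” or pattern of change over time".
- Predictors: survivor-, partner- and couple-level "determinants of fitting one pattern of change over the other(s) will be modeled using logistic, multinomial or ordinal regression as appropriate".

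On software, the Analysis Plan says only "Aim 4 will be conducted using MPlus v7.2"; it names no procedure or option. Section 13.0 does not mention predictors inside the mixture model, a bias-corrected three-step fit, posterior-probability weighting, pseudo-class draws, an entropy threshold or a rule for choosing the number of classes.

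Aim 4 is labelled exploratory in Section 2.0 and again in Section 13.0. Under Power and Sample Size the plan says "No universal approach has been adopted for sample size considerations in GMM and this will be used in an exploratory aim" and offers only a rule of thumb: "our n-to-items ratio exceeds sample size recommendations for related approaches (10-20:1)."

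**The concern.** Read in order, the steps are classify, then regress. A mixture model gives each couple a probability of belonging to each class. Modal assignment replaces those probabilities with one label, and some labels will be wrong. An ordinary regression on the label treats it as known, so misassignment enters the outcome and distorts the coefficients.

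Aim 4 is where the plan intends to say which couples gain most and to describe a possible small group who do worse, and it relies on that description to judge generalisability. Distorted coefficients could hide a real marker of benefit or harm, or give the wrong size for one.

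**Working it through.** **Inputs from the plan.** Modal assignment followed by logistic, multinomial or ordinal regression (Analysis Plan, Aim 4); 264 couples for analysis (Power and Sample Size). The plan's own inflation reproduces: 264 / 0.90 = 293.3, rounded up to 294 randomized. Aim 4 has no figure of its own to reproduce.

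**Assumed, because the plan is silent.** True odds ratio 2.0 per SD of a standard normal predictor (log-odds 0.693); class shares, class separation and number of classes as stated below.

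**Check 1: direct calculation, two classes.** With true membership probability p(x) = 1 / (1 + exp(-(a + 0.693x))) and misassignment rate e, equal in both classes, the label follows

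P(assigned to class 1 | x) = (1 - e) p(x) + e (1 - p(x)).

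Refitting a logistic slope to this by maximum likelihood over the distribution of x gives:

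| Misassigned | Apparent OR, 30% class share | Apparent OR, 50% class share |
|---|---|---|
| 5% | 1.80 | 1.84 |
| 10% | 1.65 | 1.70 |
| 20% | 1.42 | 1.48 |

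At 20%, ln 1.42 / ln 2 = 0.51 and ln 1.48 / ln 2 = 0.57, so 43-49% of the log odds ratio is lost.

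**Check 2: simulation at n = 264.** Two normal classes of about equal size, 500 replicates per row, mixture parameters known. Regression on the modal class is compared with a three-step fit that uses the classification-error matrix.

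| Entropy | Misassigned | Modal: log-odds (SE) | Share of true effect | Modal: 95% CI coverage | Corrected: log-odds (SE) | Corrected: coverage |
|---|---|---|---|---|---|---|
| 0.91 | 2% | 0.653 (0.143) | 94% | 93% | 0.691 (0.154) | 96% |
| 0.76 | 7% | 0.594 (0.140) | 86% | 87% | 0.708 (0.175) | 96% |
| 0.64 | 10% | 0.530 (0.137) | 76% | 74% | 0.707 (0.196) | 97% |
| 0.49 | 16% | 0.467 (0.134) | 67% | 59% | 0.737 (0.234) | 97% |
| 0.32 | 23% | 0.351 (0.130) | 51% | 25% | 0.718 (0.291) | 96% |

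Estimating the mixture by EM (250 replicates) gives similar shares: 0.96, 0.85 and 0.78 at entropy 0.91, 0.76 and 0.64.

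**Check 3: what drives the under-coverage.** At entropy 0.76 the modal-class SE (0.140) equals the sampling SD of the estimate (0.140). The bias is 0.693 - 0.594 = 0.099, or 0.099 / 0.140 = 0.71 SE. Bias alone would give coverage Φ(1.96 - 0.71) - Φ(-1.96 - 0.71) = 0.89; the simulation gave 0.87. At entropy 0.49 the bias is 0.226 / 0.134 = 1.69 SE, predicting 0.61 against 0.59. With no true effect, 4.2-4.8% of tests reject.

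**Check 4: when the direction changes.**

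- Two equal classes 2.5 SD apart, predictor also correlated with the outcome within class. The modal-class OR is 1.42 at a correlation of -0.2, about 2.0 at +0.2 and about 2.4 at +0.4. With no such correlation it is exp(0.530) = 1.70.
- Three classes, entropy 0.57, 21% misassigned (400 replicates). A contrast that is truly zero moves to 0.107, and the one that is truly 0.693 falls to 0.568; coverage is 89% and 87%.

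**The case against.** The best defence is that the plan never says the hard label is the regression outcome. A one-step mixture model with predictors also contains a multinomial logistic regression, and Aim 4 is placed in mixture software. This stands in part: uncorrected use of the label is inferred from silence, and a reader should not conclude that the plan excludes a corrected fit. But the order of the text, assignment first and a choice among three ordinary regressions after it, points to classify-then-regress.

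Three stronger readings are tempting and not supported.

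- *Predictor effects will always shrink.* That needs predictors to act through class membership alone and, in practice, two classes. The plan establishes neither and expressly allows multinomial outcomes. Check 4 shows no shrinkage, inflation, and movement away from zero.
- *The standard errors are wrong, so findings will be falsely positive.* The modal-class SE is below the corrected one (by 7%, 20% and 43% at entropy 0.91, 0.76 and 0.49), but it matches the spread of the biased estimate, and null rejection in two classes is not inflated.
- *The loss in this trial is known to be large.* The plan gives no classification accuracy. At entropy 0.91 the estimate keeps 94% of the effect with 93% coverage, which matters little.

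It is also fair to say that Aim 4 is exploratory and sets no sample size or confirmatory test. That lowers the priority but does not remove the bias.

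**Conclusion.** The point holds in a limited form. As written, Aim 4 makes no allowance for classification error, and its predictor effects can be biased. The bias is toward no effect when predictors act only through class membership, and possibly in either direction when they also relate to change within class or when there are three or more classes. Intervals under-cover mainly because of that bias.

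The size depends on an assumed odds ratio of 2.0 per SD and on class separation that the plan does not give: negligible at entropy about 0.9, material at about 0.76 and below. The equal error rates in Check 1 are a simplification, since modal assignment need not err equally in both classes. The extra error from feeding model-based couple estimates into the mixture was not quantified.

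A reader might infer that the trial's main conclusions are at risk. They are not: Aims 1-3 do not use the class assignments. The priority is modest.

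**What to change.** In the Aim 4 paragraph, replace regression on the modal class with one named method, fixed before the classes are seen:

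- an error-corrected three-step analysis using the classification-error matrix, or
- a one-step mixture model that includes the predictors.

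Either should allow direct predictor effects on the growth factors where indicated, because the simple three-step correction also assumes that predictors act only through class. Report entropy, average posterior probabilities by assigned class and the classification table beside the results.

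The cost is a few sentences in the plan, slightly more analysis work and wider intervals (in Check 2 at entropy 0.76, SE 0.175 rather than 0.140). No new data, visits or participants are needed.

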will lead to better physical, mental and relational health within the dyad. As a next step toward broader dissemination, we need to know if a couples-based exercise approach is similarly effective for couples coping with other cancers (and when survivor gender varies), early in the illness trajectory when a couple's relationship is most vulnerable, and at reducing risk factors for chronic illness in both partners. An equally important next step is to distinguish the unique benefits of partnered training on individual and couple health from the possible benefits of exercising in a group with others and/or of engaging both partners in a new health behavior. We propose a larger, more rigorous trial of *Exercising Together*, expanding to include couples coping early on with PC, BC or CRC, clinical markers of chronic disease risk, and comparison groups that can test the unique benefits of partnered training.

Additional background for ancillary study: Rural cancer survivors are at greater risk for a variety of poor health outcomes, even many years after their cancer diagnosis, but are the least likely to have access to programs and resources to improve their health and well-being. Improving health behaviors, such as physical activity, can have a substantial impact on quality of life and survival in cancer survivors and their partners, but rural and poor adults, and particularly cancer survivors, have low rates of physical activity. Survivors living in rural areas and/or in poverty face many barriers to exercise, particularly facility-based, supervised programs which can provide a more effective, safe and supportive engaging environment than unsupervised training. There are no studies of supervised group exercise in rural and poor cancer survivors and no studies at all, even distance-based programs, that target partners and the couple as a whole. Given our successful adaptation of *Exercising Together* to remote delivery during the COVID 19 pandemic, we may be able to extend our programs to couples coping with cancer who would never be able to participate in our parent trial.

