**Additional Analyses: Gender as a Moderating Variable:** We will also explore the moderating effect of gender on the effectiveness of *Exercising Together* in couples coping with different cancers (e.g., do women benefit more than men) after controlling for role (i.e., survivor vs spouse/partner). Interaction terms will be added to models described above to test for moderating effects.

**Ancillary study:** Feasibility and acceptability of the ancillary study will be determined by calculating accrual, retention, and adherence rates, number of adverse events, and the proportion of testing visits and surveys completed. Feasibility and acceptability metrics will be compared to those of the parent trial.

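### The exploratory gender models control for role but not cancer type, so a role-specific gender term would absorb about two thirds of any prostate-breast difference in programme effect

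*Combined protocol and SAP*

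**What the plan says.** The gender analysis is in section 13.0, under Additional Analyses. It explores moderation "in couples coping with different cancers (e.g., do women benefit more than men", and does so "after controlling for role (i.e., survivor vs spouse/partner". The method is one sentence: "Interaction terms will be added to models described above to test for moderating effects". There is no equation or list of terms, and nothing says whether gender enters once for everybody or separately for survivors and partners.

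The models to be extended are those of Aim 1: "The Level 1 model has four coefficients representing intercepts (baseline assessments) and slopes (rates of change) for survivors and spouses/partners". The general covariate rule in the Analysis Plan is "Age, comorbidities and time since diagnosis will be considered as covariates in all analyses".

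Cancer type stratifies the randomisation (sections 8.0 and 13.0), and the sample is balanced on it by design: "We will recruit approximately even numbers of couples coping with each type of cancer (N=98 per disease site". Yet no outcome model in section 13.0 contains cancer type, either alone or by arm. Section 4.0 admits same-sex couples without giving an expected share. The background (section 1.0) wants to know whether the approach works in other cancers "and when survivor gender varies".

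**The concern.** Prostate survivors are men and breast survivors almost all women, and their partners are mostly the reverse. With one third of couples per site, gender among survivors (or among partners) is therefore close to a prostate-versus-breast label in about two thirds of couples. Controlling for role does not undo this. In a model with separate survivor and partner slopes, conditioning on role is what lines gender up with cancer type. None of the listed covariates addresses it.

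Suppose the programme works differently in prostate and breast couples because of the disease, its treatment or its effect on intimacy. The gender interaction would pick up much of that difference, and it could be reported as men and women responding differently. That bears on who should be offered the programme, which the background gives as the reason for extending it beyond prostate cancer.

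**Working it through.** **The plan's own figure.** 264 couples / 0.90 = 293.3, rounded up to 294; 294 / 3 = 98 per cancer type. Both match section 13.0. The plan gives no figure for the gender analysis.

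**Assumptions, because the documents give no values.** All breast survivors are women; couples are heterosexual unless stated; colorectal survivors are half men (49 of 98). D is the prostate-minus-breast difference in programme effect, with colorectal midway and no true gender effect. The illustration takes D = 0.40 SD: effects of 0.4 in prostate, 0.2 in colorectal and 0 in breast.

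**1. Role-specific gender term, survivors.**
- Men: (98 × 0.4 + 49 × 0.2) / 147 = 49.0 / 147 = 0.333
- Women: (98 × 0 + 49 × 0.2) / 147 = 9.8 / 147 = 0.067
- Men minus women: 0.267 SD, and 0.267 / 0.40 = 0.67 D

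The fraction is 0.68 if colorectal survivors are 30% or 70% men.

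**2. Role-specific gender term, partners.** If partners share the difference, the sexes swap and the term is −0.67 D. With 5% or 10% same-sex couples it is −0.60 D or −0.53 D.

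**3. One gender term pooled over roles** (294 men, 294 women).
- Difference shared by both partners. Men: (98 × 0.4 + 98 × 0 + 98 × 0.2) / 294 = 58.8 / 294 = 0.20. Women: also 0.20. The contrast is 0, or 0.03 D to 0.07 D with 5% to 10% same-sex couples.
- Difference in survivors only. Men: 49.0 / 294 = 0.167. Women: 9.8 / 294 = 0.033. The contrast is 0.133 SD, or 0.33 D.

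In the pooled form, gender in prostate and breast couples is aliased with role-by-cancer-type, not with cancer type itself.

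**4. How often a false signal appears** (role-specific, survivors, Arm 1 versus Arm 2). Take 264 / 3 = 88 couples per arm, 44 men and 44 women survivors in each, outcome SD 1, two-sided alpha 0.05 and a simple contrast of means. SE = √(4/44) = 0.302. With D = 0.40 the term is centred on 0.267 and is significant 14% of the time instead of 5%. With D = 0.80 (centred on 0.533) it is significant 42% of the time.

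**5. Price of adjustment.** With cancer type and its arm interaction in the role-specific model, only colorectal couples inform the survivor gender term.
- Variance of gender: 0.25 overall, and 0.25 / 3 = 0.083 within cancer type. Inflation 0.25 / 0.083 = 3.0 (3.5 if colorectal survivors are 30% or 70% men).
- Per arm and sex: 88 / 3 / 2 = 14.7. SE = √(4/14.7) = 0.522.
- Interaction detectable at 80% power: 2.80 × 0.302 = 0.84 SD unadjusted; 2.80 × 0.522 = 1.46 SD adjusted.
- Power for a 0.40 SD interaction: 0.26 unadjusted, 0.12 adjusted.

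**The case against.** The strongest reply is that the size depends on a model form the plan never states. Asking whether women benefit more than men, controlling for role, reads naturally as one contrast over all 588 participants. On that reading each heterosexual couple contributes one man and one woman, gender is balanced within every cancer type, and a difference common to both partners drops out. That common difference is a plausible case for relationship outcomes. This stands: the 0.27 SD applies to survivors under a role-specific term and is not the gender estimate in general. It also limits the remedy, because in the pooled form cancer-type-by-arm terms without role interactions would change nothing in heterosexual couples. It does not remove the problem: a difference confined to survivors still comes through at 0.33 D, and the Aim 1 structure to which the interactions are added is role-specific.

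A reader might infer that gender and cancer type cannot be separated in this trial, or that role is the only adjustment. The documents support neither. Colorectal couples are a third of the sample and same-sex couples are eligible, so the aliasing is partial. Age, comorbidities and time since diagnosis are also considered, though they do not stand in for cancer type.

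It is also fair that the 0.4/0.2/0 pattern is assumed, that a purely descriptive comparison of men and women is legitimate, and that the analysis is labelled exploratory. These points lower the stakes. They do not make the gender result interpretable apart from cancer type.

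**Conclusion.** The point holds as a low-severity improvement. Followed as written within the role-specific dyad model, the gender analysis gives a term containing about 0.67 of any prostate-breast difference in programme effect, with opposite sign in partners who share that difference. In the pooled form the share is zero for a difference common to both partners in heterosexual couples, and about 0.33 for one confined to survivors. The plan has couples that could partly separate gender from cancer type but does not use them for that purpose.

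These fractions rest on equal numbers per site, colorectal effects midway between the other two, and mostly heterosexual couples. The colorectal sex split matters little. The SD figures also need an assumed 0.40 SD difference, for which the documents give no evidence either way.

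A reader might go further and conclude that every cancer-type difference would be reported as a gender effect, or that the trial's main findings are compromised. Neither follows. The first fails for a shared difference under a pooled term. The second fails because the analysis is exploratory and separate from the primary comparisons.

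**What to change.** In the gender paragraph of section 13.0:

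- State whether the gender-by-arm term is role-specific or pooled over roles.
- Add cancer type with its arm and role interactions to the gender models, or report the gender-by-arm contrast within colorectal couples alongside the planned one. The role interactions are needed if the term is pooled.
- State that the unadjusted gender contrast must not be read as separate from cancer type.

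Cancer type is already collected (section 3.0, Descriptive Measures) and used for stratification, so the change is wording and model terms only. The cost is precision: the adjusted contrast rests mainly on the colorectal third of the sample, with the roughly threefold variance and low power shown above. It should be presented as an estimate with its interval and labelled exploratory; a null result would say little.
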